### **3 STUDY DESIGN**

#### **3.1 Overall Study Design and Treatment Groups**

This study will be performed at approximately 3 to 15 study centers located in the United States and Latin America.

The study is an open-label, non-randomized, uncontrolled, multicenter, dose escalation, cohort expansion and extension study with single and multiple-dose PK in subjects with relapsed/refractory lymphomas, MF, CLL, and advanced/metastatic solid tumors for which no standard therapy exists. The study will be conducted in 2 parts:

Part A: Evaluation of the safety and tolerability of escalating multiple doses of ASN002;

Part B: Cohort expansion of 6 identified disease-specific cohorts (DLBCL, MCL, FL, PTCL, MF and CLL) from Part A to further evaluate the safety, tolerability and antitumor activity of multiple doses of ASN002.

Part A will be a “3+3” dose escalation scheme beginning with dose level 1 at a dose of 10 mg every 12 hours. Subjects will receive a single dose of ASN002 on Day 1, followed by every 12 or 24 hours, as assigned, dosing beginning on Day 3. The dose of ASN002 will be escalated to identify DLTs, and the MTD. If an MTD is not identified by the last scheduled cohort, dose escalation will continue in less than or equal to 50% increments until the MTD is identified. If supported by the PK profile, transition to once daily dosing may be considered. The starting dose of the once daily (qd) dosing cohorts will not exceed the total daily dose of the highest twice daily dose that is considered safe and well tolerated. Daily dosing cohorts may include doses beginning at 60 mg QD. Additional dose escalation may be performed for the qd dose cohorts, if the MTD is not identified by the 100 mg qd dose.

The study design includes a screening period (up to 28 days), and a DLT observation period of 28 days (Cycle 1). A subject with no DLTs during Cycle 1 will have the opportunity to continue to receive ASN002, at the discretion of the investigator. Subjects that are not able to complete Cycle 1 for reasons other than DLT will be replaced. Subjects participating in Parts B who discontinue from the study due to non-compliance or protocol violations may be replaced at the discretion of the Sponsor. Subjects may

receive treatment with ASN002 in the absence of intolerable toxicity or disease progression for up to 12 months. If the subject is not a candidate for or chooses not to participate in additional treatment cycles, an end of treatment visit will be performed. A follow-up visit will be performed at least 30 days after the last dose of study medication.

In Part A of the study, after the Safety Review Committee (SRC) has met and agreed to dose escalation, up to 3 additional subjects may be allowed in a lower cohort to gather additional PK, PD and safety data. The inclusion of these subjects will be based on agreement with members of the SRC and the Sponsor

Part B will be an expansion of the MTD cohort into 6 disease-specific groups to evaluate preliminary clinical anti-tumor activity. Each cohort will contain up to 14 subjects with DLBCL, MCL, FL, PTCL, MF, and CLL. Subjects may receive treatment with ASN002 in the absence of intolerable toxicity or disease progression for up to 12 months.

### 3.2 Summary of Scheduled Events

**Table 1: Schedule of Assessments (Part A)**

Study Procedure	Screening D (-28 to -1)	Cycle 1										Subsequent Cycles a				End of Treatment b	30-Day Follow-up		
		Days																	
		1	2	3	4	8	1 1	1 5	16	22	2 8	1	1 5	2 2	2 8				
Informed Consent	X																		
Eligibility Screening	X																		
Demographics	X																		
Medical History	X																		
Physical Examination c	X	X							X			X				X	X		
Disease History & Stage	X																		
Vital signs d	X	X	X	X	X		X		X	X	X				X	X			
Height e and weight	X	X										X			X	X			
ECOG PS	X	X										X			X				
12-lead ECG	X	X f	X	X		X		X f	X	X					X				
Pregnancy test, if applicable	X	X										X			X				
Serum Chemistry g	X	X				X		X		X					X	X			
Liver Function Tests g	X	X			X	X	X	X				X			X	X			
CBC with Diff and Platelets g	X	X				X		X		X					X	X			
Urinalysis g	X	X										X			X				
Disease Assessment h	X												X			X			
Medication Administration			X	X i	X	X	-----X-----X					X-----X							
Pharmacokinetic Sample			X	X j	X j		X j		X	X j	X j		X j						
Pharmacodynamic Sample			X				X		X				X l						
Adverse Events			X											X l					
Concomitant Medications		X-----X																	
Dispense Drug Diary				X									X						
Medication Compliance						X		X		X			X			X			

Statistical Analysis Plan  
Protocol ASN002-101

---

a Subsequent cycles should begin within 3 days of either Day1, or the previous cycle. Subjects may continue to receive additional cycles of ASN002 in the absence of intolerable or severe toxicity or disease progression. All safety laboratory and radiographic evaluations for continued dosing must be completed prior to evaluation by the investigator.

b End of Treatment Visit should take place < 1 week from the last dose of study medication.

c Complete physical examination will be conducted at screening and end of treatment. Other examinations may be brief, problem-focused examinations and review of systems.

d Vital signs will consist of heart rate, blood pressure, and temperature. Day 3 and Day 16 apply to QD dosing cohorts only.

e Height to be obtained at baseline only.

f Refer to the Schedule of Assessments Table for Day 1, and Day 15. Day 3 and Day 16 apply to QD dosing cohorts only.

g Laboratory assessments may be drawn up to 72 hours in advance of the scheduled visit for patient convenience. Refer to Error! Reference source not found. for a complete list of required safety laboratory assessments. Labs need not be repeated on day 1 cycle 1 if baseline data were obtained within the preceding 72 hours.

h Subjects will be evaluated based on malignancy-specific requirements. Evaluations may be completed up to one week prior to the nominal visit.

2014 Lugano Classification (every 12 weeks  $\pm$  1 week) or

RECIST 1.1 for advanced solid tumors every 8 weeks for the first 24 weeks, and every 12 weeks thereafter after the initiation of treatment with ASN002.

i In the QD dosing cohorts, the Day 2 dose should be omitted. All other assessments should be performed.

j PK samples are to be drawn as trough samples prior to study drug administration.

k Cycle 2, Day 1 only, prior to dose administration.

l 30-day follow up for Adverse Events may be conducted as a telephone contact.

**Table 2: Schedule of Assessments (Part B)**

Study Procedure	Screening D (-28 to -1)	Cycle 1				Subsequent Cycles a			End of Treatment b	30-day Follow Up	
		Days									
		1	2	8	15	22	1	15	22		
Informed Consent	X										
Eligibility Screening	X										
Demographics	X										
Medical History	X										
Physical Examination c	X	X					X		X	X	
Disease History & Stage	X										
Vital signs d	X	X			X		X		X	X	
Height e and weight	X						X		X	X	
ECOG PS	X	X					X		X		
12-lead ECG	X	X					X		X		
Pregnancy test, if applicable		X								X	
Serum Chemistry g	X	X		X	X		X	X		X	
Liver Function Tests g	X	X		X	X		X	X		X	
CBC with Diff and Platelets g		X		X	X		X	X		X	
Urinalysis h	X						X				
Disease Assessment i	X								X		
MPN-SAF (MF subjects only) j			X		X	X	X	X	X	X	
Medication Administration			X-----X								
Pharmacokinetic Samples			X k	X l	X l	X l		X l	X l		
Pharmacodynamic Samples			X			X		X			
Adverse Events			X-----X n								
Concomitant Medications			X-----X								
Dispense Drug Diary			X				X				
Medication Compliance							X			X	

Statistical Analysis Plan  
Protocol ASN002-101

---

a Subsequent cycles should begin within 3 days of either Day1, or the previous cycle. Subjects may continue to receive additional cycles of ASN002 in the absence of intolerable or severe toxicity or disease progression. All safety laboratory and radiographic evaluations for continued dosing must be completed prior to evaluation by the investigator.

b End of Treatment Visit should take place < 1 week from the last dose of study medication.

c Complete physical examination will be conducted at screening and end of treatment. Other examinations may be brief, problem-focused examinations and review of systems. Physical exam includes spleen measurement for subjects with MF.

d Vital signs will consist of heart rate, blood pressure, and temperature.

e Height to be obtained at baseline only.

f Refer to the Schedule of Assessments Table for Day 1, and Day 15.

g Laboratory assessments may be drawn up to 72 hours in advance of the scheduled visit for patient convenience. Refer to Error! Reference source not found. for a complete list of required safety laboratory assessments. Labs need not be repeated on day 1 cycle 1 if baseline data were obtained within the preceding 72 hours. Part B: Day 22 laboratory assessments may be omitted.

h Urinalysis is conducted on Day 1, and then as clinically indicated.

i Subjects will be evaluated based on malignancy-specific requirements. Evaluations may be completed up to one week in advance of the nominal time to accommodate scheduling.

Lymphoma: every 12 weeks by 2014 Lugano Classification.

MF: MDS-SAF questionnaire to be done weekly, spleen measurement by PE every 4 weeks for the first 24 weeks and then every 12 weeks, spleen measurement by MRI/CT to be done at baseline and on week 24.

CLL: every 8 weeks during the first 24 weeks and every 12 weeks thereafter by IWCLL criteria (and updates). A CT scan of chest/abdomen/pelvis is recommended if previously abnormal and otherwise in case of CR, a bone marrow aspirate/biopsy is recommended in case of CR or cytopenia of uncertain cause.

j The MPN-SAF questionnaire will be completed weekly while on-study. On Day 22, and during subsequent cycles a form for completion at home should be given to the subject.

k PK timepoints for Day 1 will be collected at predose, 2, 4 and 6 hours.

l Predose PK samples are to be drawn as trough samples prior to study drug administration. A trough PK sample will be drawn on Day 1 of Cycle 3, 6, 9 and 12.

m Two PK samples are requested at the end of treatment. The first may be drawn with other safety laboratory assessments. The second optional sample is drawn 2-3 hours later.

n 30-day follow up for Adverse Events may be conducted as a telephone contact.

**Table 3: Cycle 1 Serial Assessments (Part A)**

Day	Nominal Time a (hours)	Windows	Assessments b			
			PK Sample	PD Sample	ECG	VS
Day 1	Predose	Up to -60 minutes	X	X	X	X
	0.5	( $\pm$ 5 mins.)	X			
	1.0		X		X	X
	2.0		X	X	X	X
	4.0	( $\pm$ 15 mins.)	X		X	X
	8.0	( $\pm$ 1 hr)	X			
	12.0		X		X	X
Day 2	24 h post-day 1 dose	$\pm$ 1 hr from 1st dose	X		X	X
Day 3 c (QD cohorts only)	48 h post-Day 1 dose	$\pm$ 2 hr from 1 st dose	X		X	X
Day 8	Predose	N/A	X	X	X	X
Day 15	Predose	Up to -60 minutes	X	X	X	X
Day 15	0.5	( $\pm$ 5 mins.)	X			
	1.0		X		X	X
	2.0		X	X	X	X
	4.0	( $\pm$ 15 mins.)	X		X	X
	8.0	( $\pm$ 1 hr)	X			
	12.0		X		X	X
Day 16 (QD cohort only)	24 h post-Day 15 dose		X		X	X
Day 22	Pre-dose	N/A	X		X	X
Cycle 2, Day 1	Pre-dose	N/A	X	X		X

a The actual time of all assessments will be recorded in source documents and on the eCRF

b The priority of assessments for the procedures is (1) PK/PD, (2)ECG, (3)VS

c Only subjects in single daily dose cohorts require PK on Day 3 and 16.

Statistical Analysis Plan  
Protocol ASN002-101

**Table 14: PK/PD Assessments (Part B)**

Day	Nominal Time a (hours)	Windows	Assessments	
			PK Sample	PD Sample b
Day 1	Predose	N/A	X	X
	2.0	± 15 mins	X	X
	4.0	± 15 mins	X	
	6.0	± 30 mins	X	
Day 2	Predose	N/A	X	
Day 8	Predose	N/A	X	
Day 15	Predose	N/A	X	X
	2.0	± 15 mins.	X	X
Cycle 2, Day 1	Predose	N/A	X	X
	2.0	± 15 mins.	X	X
Cycle 2, Day 15	Predose	N/A	X	
Day 1, Cycle 3, 6, 9 and 12	Predose	N/A	X	
End of Treatment	N/A	N/A	X	
	2-3 (optional)	± 15 mins.	X	

a The actual time of all assessments will be recorded in source documents and on the eCRF

b In Part B of the study, only selected sites will be collecting the PD samples for phospho-proteins

## 4 SAMPLE SIZE CONSIDERATIONS

### Part A:

A traditional 3+3 design will be used to identify the MTD. In addition to the 40 subjects enrolled in the previous amendments, an additional 24 subjects may be enrolled and dose in either fed or fasted states. A total of 64 subjects will be enrolled into the Part A dose escalation phase of the study. No randomization will be performed for Part A.

Part B: A sample size of 84 subjects (14 each in DLBCL, MCL, FL, PTCL, MF, and CLL) will be enrolled. The null hypothesis that the true response rate is 0.05 will be tested against a one-sided alternative. A total of 14 patients will be accrued in each cohort. The null hypothesis will be rejected if at least 3 responses are observed in 14 subjects. This design yields a type I error rate of 0.02 and power of 0.9 when the true response rate is 0.4.

## 5 ANALYSIS POPULATIONS

### 5.1 Safety Population

The safety population includes all subjects who receive at least 1 dose of study medication. Safety analyses will be conducted against the safety population. The safety population will apply to Parts A and B.

### 5.2 Efficacy Population (EP)

The efficacy population (EP) will include all subjects who have an evaluable screening and post-dose tumor assessment. The EP will be used as the supportive analysis population for summaries and analyses of the efficacy endpoints. No EP will be reflected if Part B is not completed for at least one indication.

### 5.3 Per-Protocol (PP) Population

The PP population includes all EP subjects without major protocol deviations. The PP population will be used as the primary analysis population for efficacy summaries and analyses. No PP will be reflected if Part B is not completed for at least one indication.

## 6 CONSIDERATIONS FOR DATA ANALYSIS

### 6.1 Programming Environment

All analyses will be conducted using SAS® version 9.3.

### 6.2 Strata and Covariates

There are no other planned strata or covariates for the analysis of this study.

### 6.3 Subgroups

There are no planned subgroup analyses.

### 6.4 Multiple Comparisons and Multiplicity

There are no planned adjustments for multiple hypothesis testing.

## **6.5 Significance Level**

Unless otherwise specified, all statistical analyses will be conducted using a one-sided significance level ( $\alpha$ ) of 0.05 and one-sided hypothesis testing.

## **6.6 Statistical Notation and Methodology**

Unless stated otherwise, the term “descriptive statistics” refers to the number of subjects (n), mean, median, standard deviation, minimum, and maximum for continuous data and frequencies (counts and percentages) for categorical data. Unless otherwise noted, all data collected during the study will be included in subject data listings and will be sorted by study component (i.e., Part A, and Part B), dosing cohort, subject number, and date/time within each subject.

# **7 DATA HANDLING METHODS**

## **7.1 Missing Data**

### **7.1.1 Date Values**

The missing component(s) of incomplete dates (e.g. start and/or stop dates of AE, concomitant medication, medical history) will be assumed as the most conservative value possible. For example, if the start date has a missing day value, the first day of the month will be imputed for study day computations, etc. If day is missing for an end date, the last day of the month will be imputed. Similar logic will be assumed for missing month and year components. For determination of treatment-emergent status, the start date will be imputed as the date of the first dose of study drug.

Date imputation will only be used for computational purposes such as treatment-emergent status, etc. Actual data values, as they appear in the original CRFs, will be presented in the subject data listings.

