## **12.5 Reporting Adverse Events and Serious Adverse Events**

### **12.5.1 Reporting Adverse Events**

Throughout the study, AEs will be documented on the source document and on the appropriate page of the eCRF whether or not considered treatment-related. This includes any new signs, symptoms, injury or illness, including increased severity of previously existing signs, symptoms, injury, or illness. Conditions existing prior to screening will be recorded as part of the subject's medical history. The investigator is responsible for assessing the relationship of AEs to the study medication; relationship will be classified as not related, possibly related, or probably related.

All AEs will be collected by the investigator from the time of signing the informed consent through 30 days after the last dose of ASN002; this includes any AEs that are ongoing at the time of completion/termination of the study. All ongoing AEs must be followed until resolution or for 30 days after the subject's last study visit, whichever comes first.

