### 15.5.4 Adverse Events

The Medical Dictionary for Regulatory Activities (MedDRA, version 17.0 or higher) will be used to code AEs.

An AE (classified by preferred term) that started during the treatment period will be considered a TEAE if it was not present prior to the first dose of study drug, or was present prior to the first dose of study drug but increased in intensity during the treatment period. If more than 1 AE is reported prior to the first dose of study drug and coded to the same preferred term, then the AE with the least intensity will be used as the benchmark for comparison to the AEs occurring during the treatment period which were also coded to that preferred term. Any AE present prior to the first dose of study drug that increases in intensity during the treatment period will be re-entered with a new start date of the date of increased intensity. An AE that occurs more than 30 days after the last dose of study drug will not be counted as a TEAE.

Descriptive statistics (the number and percentage) for subjects reporting TEAEs will be tabulated by system organ class, preferred term, and dose level. If more than 1 AE is coded to the same preferred term for the same subject, the subject will be counted only once for that preferred term.

The incidence of TEAEs by severity and relationship to study drug will be summarized by system organ class, preferred term, and dose level. If more than 1 AE is coded to the same preferred term for the same subject, the subject will be counted only once for that preferred term using the most severe and most related occurrence for the summarization by severity and by relationship to the study drug respectively. The incidence of TEAEs will also be summarized by preferred term and dose level and sorted by decreasing frequency. SAEs and AEs leading to premature discontinuation of study drug will be summarized by preferred term and dose level, and sorted by decreasing frequency for dose level.

Descriptive statistics (the number and percentage) for subjects reporting TEAEs will be tabulated by system organ class, preferred term, and dose level. If more than 1 AE is coded to the same preferred term for the same subject, the subject will be counted only once for that preferred term.

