## DEFINITIONS OF TERMS

Part A	Part A, the dose escalation component of this study, will evaluate the safety and tolerability of ASN002 (study drug) including dose-limiting toxicities (DLT) and to determine the maximum tolerated dose (MTD).
Part B	Part B, the cohort expansion component of this study, will evaluate the safety, tolerability, and preliminary efficacy of ASN002 in subjects with relapsed/refractory diffuse large B-cell lymphoma (DLBCL), follicular lymphoma (FL), mantle cell lymphoma (MCL), peripheral T-cell lymphoma (PTCL), myelofibrosis (MF), and chronic lymphocytic leukemia (CLL).
Safety population	The safety population will include all subjects who take at least 1 dose of study medication. Safety analyses will be conducted using the safety population. The safety population will apply to Parts A and B.
Efficacy population	The efficacy population (EP) will include all subjects who have an evaluable screening and post-dose tumor assessment. The EP will be used as the supportive analysis population for efficacy endpoints.
PP population	The Per Protocol (PP) population will include all EP subjects without major protocol violations. The PP population will be used as the primary analysis population for efficacy.
Treatment Cohort	
There are nine treatment cohorts planned for Part A of this study:
 

Treatment Cohort 1 – 10 mg ASN002 q12H

Treatment Cohort 2 – 20 mg ASN002 q12H

Treatment Cohort 3 – 30 mg ASN002 q12H

Treatment Cohort 4 – 40 mg ASN002 q12H

Treatment Cohort 5 – 50 mg ASN002 q12H

Treatment Cohort 6 – 75 mg ASN002 q12H

Treatment Cohort 7 – 100 mg ASN002 q12H

Treatment Cohort 4a – 80 mg q24H

Treatment Cohort 5a – 120 mg q24H

Treatment-emergent	Symptoms or conditions with onset after the first administration of ASN002.

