## **10.3 Prior, Concomitant, and Post-Treatment Medications**

Medication usage will be coded using the World Health Organization (WHO) Drug Dictionary. Medication use will be presented for the Safety population by WHO Drug Anatomical/Therapeutic/Chemical (ATC) category and WHO Drug preferred name. Medication use summaries will be presented for prior medication use (prior to first administration of study drug), concomitant medication use (between the date of first administration of study drug, but not beyond the date of the last administration of study drug), and post medication use (superseding the date of last administration of study drug). Summaries will be provided by treatment cohort and overall. Medications with partial start and/or stop dates, which cannot be definitely categorized as prior, concomitant, or post-treatment medications will be considered concomitant.

All summaries will present the number and percentages of subjects using each medication by treatment cohort. The denominators for percentages will be the number of subjects in the analysis population for the treatment cohort summarized.

Prior, concomitant, and post medications will be provided in separate data listings by subject.

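### Read as written, SAP 7.1.1 gives an incomplete AE start date the first-dose date for treatment-emergent status even when the recorded month, year or stop date rules that out, so TEAE tables can over-count

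*SAP*

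**What the plan says.** SAP 7.1.1 (Date Values) opens with a general principle: "The missing component(s) of incomplete dates (e.g. start and/or stop dates of AE, concomitant medication, medical history) will be assumed as the most conservative value". For start dates it gives an example: "if the start date has a missing day value, the first day of the month will be imputed for study day computations, etc". A separate sentence then deals with treatment-emergent status: "For determination of treatment-emergent status, the start date will be imputed as the date of the first dose of study drug". The section adds that "Date imputation will only be used for computational purposes such as treatment-emergent status, etc", and that listings show the values as entered on the case report form.

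Three other places bear on the rule:

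- Protocol 12.5.1 sets the collection period: "All AEs will be collected by the investigator from the time of signing the informed consent through 30 days after the last dose of ASN002". SAP 7.2 places screening on Days -28 to -1, so pre-dose AEs will be in the database.
- Protocol 15.5.4 counts an AE that started in the treatment period as a TEAE "if it was not present prior to the first dose of study drug", or if it was present before and increased in intensity. It excludes events occurring more than 30 days after the last dose. The SAP's Definitions of Terms is shorter: "Symptoms or conditions with onset after the first administration of ASN002".
- SAP 10.3 has a conditional rule for medications: "Medications with partial start and/or stop dates, which cannot be definitely categorized as prior, concomitant, or post-treatment medications will be considered concomitant".

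**The concern.** A default to first dose is reasonable when a partial date leaves it open whether onset came before or after dosing. Here the default is stated without that condition. It replaces the whole start date, so a recorded month that proves onset before dosing, or a stop date before dosing, is not used. The same wording pulls back an event whose recorded month lies beyond the 30-day limit after last dose.

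Such events fail the protocol's TEAE definition, but the first paragraph of Protocol Section 15 gives the SAP priority where the two differ. At stake is the accuracy of the TEAE incidence tables by cohort in SAP 10.1. Safety and tolerability belong to the primary objective of both parts, and the cohorts are small.

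**Working it through.** The documents give no figure to reproduce. The check applies the rules to example dates, which are assumptions, and then looks at what can be said about size.

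**Lower end of the window.** Assume first dose on 10 March 2017 and an AE start recorded as Feb 2017, day missing. SAP 7.3 defines Study Day as date minus first-dose date before dosing, and as that difference plus 1 from first dose onward.

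- General rule in 7.1.1: start = 1 Feb 2017. From 1 Feb to 10 March is 28 + 9 = 37 days, so Study Day = -37.
- Treatment-emergent rule in 7.1.1: start = 10 March 2017, so Study Day = 0 + 1 = 1.
- Latest onset that the record allows: 28 Feb 2017, which is Study Day -10.

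No day in the recorded month is compatible with onset on or after first dose, yet the event is classified as if it began on Day 1. If it later worsened on treatment, Protocol 15.5.4 has it re-entered with a new start date. The pre-dose record is therefore not needed to capture worsening.

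**Upper end of the window.** Keep the same first dose and assume last dose on 20 April 2017, so the 30-day limit is 20 May 2017. Take an event recorded as Jun 2017. Its earliest possible onset is 1 June, which is 10 + 31 + 1 = 42 days after last dose. Protocol 15.5.4 excludes it, but the SAP sentence moves it to 10 March. Such records can exist: Protocol 12.5.2 requires serious events judged related to study drug to be reported however late they occur.

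**Comparison with medications.** SAP 10.3 uses its default only when the partial date cannot settle the category. SAP 7.1.1 has no such clause for AEs, and no other section supplies one.

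**How often the calendar permits the lower-end case.** The count ran over all first-dose dates from 31 March 2015 to 31 March 2018 (the protocol's estimated study period), weighted equally, with a full 28-day screening period. About 48% of screening days fall in an earlier calendar month than first dose (0% to 100%, depending on the day of the month). About 92% of first-dose dates have at least one such day. These figures describe the calendar only. They do not say how many AE dates are partial.

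**Effect of one misclassified subject on one table row.** The shift is 1/n:

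- n = 3: 33 percentage points
- n = 6: 17 points
- n = 14: 7 points

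This applies only if the subject has no other TEAE in that row, because SAP 10.1 counts each subject once per preferred term or system organ class. The any-TEAE row would move little: Protocol 6.3 reports 24 of 27 patients (89%) already with at least one TEAE. Rows for single terms are more sensitive. The same section lists terms seen in more than 10% of subjects, and ten of them stand at 3 of 27 (11%). One subject fewer gives 2/27 = 7.4%, below the cut.

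**The case against.** The best defence is textual. The paragraph opens by speaking of the missing components of a date, so a careful programmer might keep a known month and use first dose only where the record leaves doubt. SAP Section 14 says that nothing was changed from the protocol, which points the same way. This shows that a sensible reading is available. It does not remove the problem, because the operative sentence replaces the start date as a whole and states no limit.

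Other objections stand and narrow the point:

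- **Exposure is limited.** Conditions existing before screening are medical history (Protocol 12.5.1). At the lower end, only AEs arising between consent and first dose are affected, and only if the start date is incomplete and the recorded parts or stop date show pre-dose onset. Subjects are asked about AEs at every visit.
- **The error is visible and errs on the cautious side.** Over-counting TEAEs is conservative for safety, and listings keep the actual dates. But caution justifies a default when onset is uncertain, not the overriding of a record that settles it.
- **Dose decisions do not depend on it.** They rest on safety review committee assessment of each cohort's first 28 days (Protocol 8.5.1), and SAP 11.1 provides a by-subject listing of dose-limiting toxicities.

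A reader might also infer the opposite bias. The SAP definition requires onset after first administration, so a strict program could drop events imputed to the first-dose date. The documents do not support this as a likely outcome: a sentence written to settle treatment-emergent status by imputing first dose is evidently meant to include those events. The mismatch is worth tidying, but it is not evidence of under-counting.

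**Conclusion.** The point holds as a minor error in a stated rule. Applied as written, SAP 7.1.1 counts as treatment-emergent some AEs whose recorded dates place them outside the protocol's window, at either end. The likely direction is over-counting in the TEAE incidence tables.

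The total effect cannot be estimated, because it depends on the number of partial dates, and it may be small. A reader might take the 17 to 33 points for cohorts of 3 to 6 as the expected distortion. The documents do not support that: it is a per-subject reciprocal that holds only when the subject has no other event in the row, and Protocol 8.1 allows up to 3 additional subjects in a lower cohort, so cohorts can exceed 6. Nor do they support an inference that the maximum tolerated dose is at risk.

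The conclusion rests on reading the treatment-emergent sentence literally, and on some AE start dates being incomplete.

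**What to change.** In SAP 7.1.1, make the default conditional. Impute the first-dose date for treatment-emergent status only when the recorded parts of the start date, together with the stop date, are compatible with onset between first dose and 30 days after last dose. Otherwise keep the recorded month or year under the general first-of-month rule and classify accordingly.

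In the SAP's Definitions of Terms, align treatment-emergent with Protocol 15.5.4: not present before first dose, or present and increased in intensity during treatment, through 30 days after last dose. State that an imputed start on the first-dose date counts as treatment-emergent.

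The cost is two or three sentences in the SAP and a small change to the derivation code. Data collection and study conduct do not change.
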